6.2 Secondary objective

The secondary efficacy objectives of this study are:

- To assess the efficacy of DFV890 to improve the signs and symptoms of FCAS.
- To assess the effect of DFV890 on patient reported outcomes.

6.2.1 Variables

The secondary efficacy variables of this study are:

- Physician global assessment of autoinflammatory disease activity.
- Physician's severity assessment of autoinflammatory disease signs and symptoms.
- Patient's global assessment of disease activity.

6.2.2 Descriptive analyses

Summary tables, including absolute and relative (%) frequencies of the different categories, will be provided by period and time for each secondary variable.

Overlaying individual plots (line plots) with the screening and treatment periods in separate panels will be provided for each secondary variable. Data from -2 to 23 hours post-challenge will be considered.

6.3 Exploratory objectives

Commercially Confidential Information

Commercially Confidential Information

7 Statistical methods for safety and tolerability data

All participants within the Safety analysis set will be included in the safety data analysis.

The assessment of safety and tolerability of DFV890 is one of the secondary objectives of this study.

7.1 Variables

Adverse events, vital signs (blood pressure, pulse rate, body temperature), ECG intervals, laboratory measurements, as well as participant demographics, baseline characteristics, and treatment information.

7.2 Descriptive analyses

Participant disposition, demographics and other baseline characteristics

The disposition information for each study phase will be listed by participant. The number and percentage (%) of participants who completed each study phase and who prematurely discontinued each study phase along with the primary reason for discontinuation will be presented by period.

All data for background and demographic variables including baseline disease characteristics and smoking status will be listed by participant and summary statistics will be provided. Summary tables for categorical data will include absolute and relative frequencies. The following variables will be included in the demographics and other baseline characteristics summary table:

- Age
- Age categories (≤ 65 years old & > 65 years old)
- Sex
- Race
- Ethnicity
- Weight
- Height
- BMI
- Country

Other variables may also be considered, as needed.

Screening failures (and the reasons for those) will be listed separately.

Data on informed consent and withdrawal of informed consent will also be listed separately.

Relevant medical histories and current medical conditions at baseline will be listed and summarized by system organ class and preferred term.

Treatment

All data for study drug administration will be listed by participant. The duration of exposure to study treatment in days will be summarized. The duration of exposure to study treatment in days will be calculated as *study day of last non-missing dose – study day of first dose + 1*.

Concomitant medications and significant non-drug therapies prior to and after the start of the study treatment will be listed according to the Anatomical Therapeutic Chemical (ATC) classification system. Concomitant medications will also be summarized by medication class and preferred term.

Vital signs

All vital signs data will be listed by period, participant, and time and if ranges are available, abnormalities (and relevant orthostatic changes) will be flagged. Summary statistics will be provided by period and time.

ECG evaluations

All single 12-lead ECG data (included but not limited to PR, QRS, QT, QTcF and RR intervals) will be listed by period, participant and time, abnormalities will be flagged. Summary statistics will be provided by period and time.

Clinical laboratory evaluations

All laboratory data will be listed by period, participant, and time and if normal ranges are available abnormalities will be flagged. A separate listing is provided presenting all parameters in a participant with any abnormal values.

Summary statistics will be provided by period and time. Shift tables using the low/normal/high/ (low and high) classification will be used to compare baseline (defined as Day 1 pre-first dose assessment) to the worst on-treatment value.

Adverse events

All information obtained on adverse events will be displayed by period and participant. Two separate listings for serious adverse events and adverse events leading to study discontinuation will also be provided.

The number and percentage of participants with adverse events will be tabulated by body system and/or preferred term with a breakdown by period. An adverse event starting in one period and continuing into the next period is counted only in the onset period. A participant with multiple adverse events within a body system and period is only counted once towards the total of this body system and period.

The number and percentage of participants with skin rash will be summarized by period. Skin rash data will also be listed.

Separate summaries will be provided for AEs by maximum severity, drug-related AEs, serious AEs, drug-related serious AEs and cold challenge-related AEs by body system and preferred term with a breakdown by period.

The overall incidence of AEs including the number of events and the number (and percentage) of participants under specific AE categories will also be summarized by period in a separate table.

For the legal requirements of ClinicalTrials.gov and EudraCT, two tables are required: on treatment emergent adverse events which are not serious adverse events with an incidence greater than 5% and on treatment emergent serious adverse events and SAE suspected to be related to study treatment will be provided by system organ class and preferred term on the safety analysis set.

If for a same participant, several consecutive AEs (irrespective of study treatment causality, seriousness and severity) occurred with the same SOC and PT:

- a single occurrence will be counted if there is ≤ 1 day gap between the end date of the preceding AE and the start date of the consecutive AE
- more than one occurrence will be counted if there is > 1 day gap between the end date of the preceding AE and the start date of the consecutive AE.

For occurrence, the presence of at least one SAE / SAE suspected to be related to study treatment / non SAE has to be checked in a block e.g., among AE's in a ≤ 1 day gap block, if at least one SAE is occurring, then one occurrence is calculated for that SAE.

The number of deaths resulting from SAEs suspected to be related to study treatment and SAEs irrespective of study treatment relationship will be provided by SOC and PT. All information obtained on deaths will be listed.

Other safety evaluations

Cold challenge

All cold challenge data (challenge start and end datetime, temperature of cold room at start and end time ($^{\circ}$ C) and reason for interruption of the cold challenge) will be listed by participant.

Commercially Confidential Information

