10.1 Definition of adverse events and reporting requirements

10.1.1 Adverse events

An adverse event (AE) is any untoward medical occurrence (e.g. any unfavorable and unintended sign [including abnormal laboratory findings], symptom or disease) in a clinical investigation participant after providing written informed consent for participation in the study. Therefore, an AE may or may not be temporally or causally associated with the use of a medicinal (investigational) product.

The investigator has the responsibility for managing the safety of individual participant and identifying AEs.

Novartis qualified medical personnel will be readily available to advise on trial related medical questions or problems.

The occurrence of AEs must be sought by non-directive questioning of the participant at each visit during the study. AEs also may be detected when they are volunteered by the participant during or between visits or through physical examination findings, laboratory test findings, or other assessments.

AEs must be recorded under the signs, symptoms, or diagnosis associated with them, accompanied by the following information (as far as possible) (if the event is serious refer to [Section 10.1.2](#)):

1. The severity grade
 - mild: usually transient in nature and generally not interfering with normal activities
 - moderate: sufficiently discomforting to interfere with normal activities
 - severe: prevents normal activities
2. Its relationship to the study treatment. If the event is due to lack of efficacy or progression of underlying illness (i.e. progression of the study indication) the assessment of causality

will usually be 'Not suspected.' The rationale for this guidance is that the symptoms of a lack of efficacy or progression of underlying illness are not caused by the trial drug, they happen in spite of its administration and/or both lack of efficacy and progression of underlying disease can only be evaluated meaningfully by an analysis of cohorts, not on a single participant

3. Its duration (start and end dates) or if the event is ongoing, an outcome of not recovered/not resolved must be reported
4. Whether it constitutes a SAE (see [Section 10.1.2](#) for definition of SAE) and which seriousness criteria have been met
5. Action taken regarding with study treatment. All AEs must be treated appropriately. Treatment may include one or more of the following:
 - Dose not changed
 - Dose reduced/increased
 - Drug interrupted/withdrawn

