6. Its outcome (i.e. recovery status or whether it was fatal)

Conditions that were already present at the time of informed consent should be recorded in medical history of the participant.

AEs (including lab abnormalities that constitute AEs) should be described using a diagnosis whenever possible, rather than individual underlying signs and symptoms.

AE monitoring should be continued until the end of the study visit.

Once an AE is detected, it must be followed until its resolution or until it is judged to be permanent (e.g. continuing at the end of the study), and assessment must be made at each visit (or more frequently, if necessary) of any changes in severity, the suspected relationship to the interventions required to treat it, and the outcome.

Information about adverse drug reactions for the investigational drug can be found in the IB.

Abnormal laboratory values or test results constitute AEs only if they fulfill at least one of the following criteria:

- they induce clinical signs or symptoms
- they are considered clinically significant
- they require therapy

Clinically significant abnormal laboratory values or test results must be identified through a review of values outside of normal ranges, significant changes from baseline or the previous visit, or values which are considered to be non-typical in participant with the underlying disease.

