10.1.2 Serious adverse events

An SAE is defined as any AE [appearance of (or worsening of any pre-existing)] undesirable sign(s), symptom(s), or medical conditions(s) which meets any one of the following criteria:

- fatal
- life-threatening

Life-threatening in the context of a SAE refers to a reaction in which the participant was at risk of death at the time of the reaction; it does not refer to a reaction that hypothetically might have caused death if it were more severe (please refer to the ICH-E2D Guidelines).

- results in persistent or significant disability/incapacity
- constitutes a congenital anomaly/birth defect
- requires inpatient hospitalization or prolongation of existing hospitalization, unless hospitalization is for:
 - routine treatment or monitoring of the studied indication, not associated with any deterioration in condition
 - elective or pre-planned treatment for a pre-existing condition that is unrelated to the indication under study and has not worsened since signing the informed consent
 - social reasons and respite care in the absence of any deterioration in the participant's general condition
 - treatment on an emergency outpatient basis for an event not fulfilling any of the definitions of a SAE given above and not resulting in hospital admission
- is medically significant; e.g. defined as an event that jeopardizes the participant or may require medical or surgical intervention to prevent one of the outcomes listed above

Medical and scientific judgment should be exercised in deciding whether other situations should be considered serious reactions, such as important medical events that might not be immediately life threatening or result in death or hospitalization but might jeopardize the participant or might require intervention to prevent one of the other outcomes listed above. Such events should be considered as "medically significant." Examples of such events are intensive treatment in an emergency room or at home for allergic bronchospasm, blood dyscrasias, or convulsions that do not result in hospitalization or development of dependency or abuse (please refer to the ICH-E2D Guidelines).

All new malignant neoplasms will be assessed as serious under "medically significant" if other seriousness criteria are not met and the malignant neoplasm is not a disease progression of the study indication.

Any suspected transmission via a medicinal product of an infectious agent is also considered a serious adverse reaction.

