1.4 Study design and treatment

This is an open-label, single-arm, multiple dose, phase II study to assess safety, tolerability and efficacy of DFV890 in participants with FCAS who show evidence of inflammatory activity after the cold challenge performed during screening. Approximately 6 participants with FCAS and confirmed NLRP3 gain-of-function mutations will be enrolled in the study.

Figure 1-1 summarizes the study design and shows the steps that will be followed in the study. The study consists of three periods: screening, treatment and follow-up.

Figure 1-1 Study Design Schematic

* Up to 12 months for participants with a historical screening cold challenge prior to protocol amendment 04.

Screening period: A period of up to 6 months (and up to 12 months for participants with a historical screening cold challenge prior to protocol amendment 04), when the participant's eligibility will be assessed at a screening visit and a cold challenge will be performed. During the screening cold challenge, participants will be domiciled for three days following a minimum of one week of recovery from the cold challenge prior to enrollment and initiation of treatment. The screening cold challenge can be conducted any time during the screening period, provided that Day 1 is conducted within 6 months (and within 12 months for participants with a historical screening cold challenge prior to protocol amendment 04; see below) of the Screening visit and all inclusion and none of the exclusion criteria are met. Historical screening cold challenge conducted in this study under the previous protocol version is acceptable, provided that Day 1 is conducted within 12 months of the Screening visit, and all inclusion and none of the exclusion criteria based on this amendment are met.

Treatment period: Eligible participants (defined as those participants who respond to the cold challenge) will then enter the treatment period where they will be administered oral DFV890 100 mg b.i.d. for 3 days, one last dose will be administered in the morning of Day 4 followed by a cold challenge. Participants will be admitted to the clinic in the morning of Day 3 (the day prior to cold challenge) and will be domiciled for a total of three days or longer (if needed). On the morning of Day 4, pre-challenge assessments will be performed, and then cold challenge

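### SAP 7.2 counts a continuing adverse event only in its onset period, with no exception for worsening, so an event that starts before dosing and worsens on DFV890 may be missing from the treatment-period counts

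*SAP*

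**What the plan says.** The columns of the adverse event (AE) tables are the study periods. SAP 1.4 defines them: "The study consists of three periods: screening, treatment and follow-up".

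SAP 7.2 tabulates the number and percentage of participants with AEs by body system and/or preferred term, broken down by period. The counting rule follows at once: "An adverse event starting in one period and continuing into the next period is counted only in the onset period". Neither SAP 7.2 nor protocol 12.5.1 says what happens if a continuing event gets worse.

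Further summaries are then planned, also by period: "Separate summaries will be provided for AEs by maximum severity, drug-related AEs, serious AEs, drug-related serious AEs", and cold challenge-related AEs. The onset-period sentence is not repeated for them, and no other assignment rule is given.

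The two registry tables in SAP 7.2 cover *treatment emergent* events. No definition of that term is visible. After these tables, the SAP merges consecutive records with the same system organ class and preferred term into one occurrence when the gap is at most 1 day, whatever their causality, seriousness or severity. It does not say which onset date or period the merged block takes.

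On data collection, protocol 10.1.1 defines an AE as an occurrence "in a clinical investigation participant after providing written informed consent for participation in the study", so AEs exist from screening onward. A detected AE is followed to resolution, and "assessment must be made at each visit (or more frequently, if necessary) of any changes in severity". Conditions already present at consent go to medical history.

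The listings are complete: "All information obtained on adverse events will be displayed by period and participant".

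**The concern.** The trial has no control arm. In the AE tables, the screening column is the only pre-drug reference for the treatment column, and safety and tolerability is a secondary objective.

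A rule that assigns an event by onset date alone answers the question of when the event began. The safety question is whether anything got worse after the first dose. For an event that is mild before dosing and more severe on drug, the two questions have different answers, and the SAP gives only the first.

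The case is plausible in this population. Protocol 1.1 describes daily rash, headache, myalgia and fatigue in many patients with FCAS. Section 3 lets screening be used to stop IL-1 therapy, and inclusion criterion 7 requires disease activity above minimal. Rash is also a recognised risk of DFV890 (protocol 4.6.3), and SAP 7.2 summarises it by period. A post-consent rash that is ongoing at Day 1 and then worsens is the kind of event in question.

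The SAP already treats laboratory data differently: shift tables compare the Day 1 pre-dose value with the worst on-treatment value. AEs have no counterpart. Within the protocol, section 10.1.2 includes worsening of an existing condition in its definition of a serious AE.

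**Working it through.** No figure in the plan is at issue, so there is none to reproduce. The check follows one event through the planned outputs and then sizes the shift.

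**Inputs**
- Periods used as columns: screening, treatment, follow-up (SAP 1.4).
- Counting rule: onset period only (SAP 7.2).
- AE collection starts at consent (protocol 10.1.1).
- Safety set: everyone who received any study drug (SAP 4).
- Participants: about 6, not more than 10 (protocol 5 and 9.1.1.1).
- Assumption: one participant has an AE that starts after consent, is mild and ongoing at first dose, and becomes severe on DFV890. The documents give no frequency for this.

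**Step 1: one record or two?** Protocol 10.1.1 has an AE followed as one event with its severity reassessed. It does not tell sites to open a new record on worsening, and it does not forbid it.

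**Step 2: if it stays one record**

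| Output | Screening | Treatment | Basis |
|---|---|---|---|
| Body system / preferred term table | 1 | 0 | Stated rule |
| Maximum severity, drug-related and serious summaries | possibly 1 | possibly 0 | Inference: no rule given |
| Registry tables | open | open | *Treatment emergent* undefined |
| AE listings | event shown in full | | Stated |

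**Step 3: if a second record is opened on worsening.** Its onset is in the treatment period, so the onset-period rule places it there and the by-period table is right. In the occurrence counts, however, the two records share a term and a gap of at most 1 day, so they merge. The period of the merged block is not stated.

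**Step 4: size in the body system / preferred term table, one-record case.** The treatment column is k/n.
- As written, n = 6: 0/6 = 0%. Exact 95% upper limit: 1 − 0.025^(1/6) = 45.9%.
- With post-dose worsening counted, n = 6: 1/6 = 16.7%. Exact 95% interval: 0.4% to 64.1%.
- Shift: 16.7 − 0 = 16.7 percentage points. At n = 10: 1/10 = 10.0 points.

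The screening column stays at 1/n in both versions, because the event did begin there. The comparison in this table therefore goes from 1/6 against 0/6 to 1/6 against 1/6 (screening against treatment).

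**Step 5: size in the maximum-severity summary, if the onset rule also governs it.** The severe row reads screening 1/6, treatment 0/6. Assigning each grade to the period in which it occurred gives screening 0/6, treatment 1/6. Only here would both columns move, and only under that inference.

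**The case against.** The strongest reply is that the SAP says nothing about worsening, so the problem depends on how sites enter data. The provision for consecutive records that may differ in severity, seriousness or causality suggests that back-to-back records of one term are expected. If worsening is entered that way, the new record has an on-treatment onset and is counted correctly by period. This stands as a possibility. It does not close the gap, because no visible text instructs sites to do so and the merging rule leaves the block's period open.

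A reader might infer that the SAP removes drug-aggravated harm from the report, puts its grade and drug attribution under screening, and so biases the comparison towards DFV890 in both columns. The documents do not support that:
- The onset-period sentence is attached to the body-system and preferred-term table. Its reach to the other summaries is an inference.
- In that table the screening count is not inflated; only the treatment count is short.
- The event stays in the listings, serious AEs and AEs leading to study discontinuation have their own listings, and skin rash has a summary and a listing. With 6 to 10 participants, each event can be read individually, and a drug-related event in a pre-drug column would stand out.
- The AE tables are descriptive. No test between periods is visible, and screening of up to 6 months (12 for historical challenges) against 5 days of treatment is already a poor incidence comparison.

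Exposure is also limited. A condition present at consent belongs to medical history, so if it worsens on drug and is reported as an AE, its onset is after dosing. FCAS episodes typically resolve within 24 hours (protocol 1.1), and at least one week of recovery separates the screening challenge from Day 1. Only AEs that arise between consent and first dose and are still ongoing at first dose are affected.

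These points reduce the weight of the issue. None of them supplies the missing rule, and complete listings do not correct the tabulated counts.

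**Conclusion.** The concern holds as a gap with a predictable direction. Under the stated rule, a screening-onset AE that stays one record and worsens after the first dose adds nothing to the treatment column of the body-system and preferred-term table. The same displacement may occur in the maximum-severity, drug-related and serious AE summaries. The registry tables cannot be judged until *treatment emergent* is defined.

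Each such participant is worth 16.7 percentage points with 6 participants and 10.0 with 10. Where it occurs, it lowers the apparent on-treatment rate. This rests on two assumptions: that worsening does not generate a new record, and that at least one such event occurs. The documents establish neither.

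The consequence is a misplaced count in descriptive tables, recoverable from the listings. The change is worth making because it is cheap and gives a better rule for a secondary objective.

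**What to change.** In SAP 7.2, replace the onset-period sentence with a rule along these lines:
- Count an AE in the treatment period if it starts, increases in severity or becomes serious on or after the first dose. Name the end of the treatment period, so that an event that first worsens in follow-up is handled on the same principle.
- Show the pre-dose grade under screening, and the post-dose maximum grade and relatedness under treatment. Apply this to all by-period AE summaries.
- Define *treatment emergent* in the same way for the registry tables.
- State which period a merged block of records (gap of at most 1 day) takes.

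The cost is a short SAP amendment before database lock and a programming flag. Sites already have to assess severity changes under protocol 10.1.1. Whether the database stores a dated grade is not visible; if it does not, the few affected events would need that date from source records. The downside is that a few events appear in two columns, which a footnote can explain.

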Study design	
This is an open-label, single-arm, multiple dose, phase II study to assess safety, tolerability and clinical efficacy of DFV890 in participants with FCAS. The study includes three periods:
 
• Screening period including a screening cold challenge up to 6 months (and up to 12 months for participants with a historical screening cold challenge prior to protocol amendment 04)• Treatment period including a second cold challenge (total of 5 days duration)• Follow up period concluded with a Study completion visit (10 days after dose administration) 
At most, the study will last up to 7 months (and up to 13 months for participants with a historical screening cold challenge prior to protocol amendment 04)

Study population	Approximately 6 adult male or female participants with FCAS, who show evidence of inflammatory activity after the cold challenge performed during screening, will be included into the study

Key Inclusion criteria	
Written informed consent must be obtained before any study-specific assessment is performedMale and female participants aged between 18-80 years inclusive (for France 18-60)Body mass index within the range of 18-35 kg/m²Participants with a genetic diagnosis of FCASParticipants with a clinical history and investigations consistent with FCAS, in the absence of a history or diagnosis of amyloidosis and/or organ damage (e.g. deafness, periorbital edema, lymphadenopathy, and serositis)Participants who have evidence of inflammatory activity after the screening cold challenge, as assessed by a relative increase in WCC of at least 40 % compared to pre-challengeEvidence of inflammatory disease activity during the screening period before the admission to the screening cold challenge, captured by the Physician global assessment of autoinflammatory disease activity > minimal, recorded at Screening Cold Challenge Admission visit

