. The overall incidences of reported AE and SAE were similar between the DFV890 and SoC groups with no unexpected or new safety findings in this COVID-19 population. There were no events related to the musculoskeletal/connective tissue systems for DFV890 or SoC arms and no unexpected renal events or serious infections in hospitalized COVID-19 population. There was as anticipated a higher incidence of mild to moderate rash events observed in participants who received DFV890. Maculopapular/pruritic skin rashes considered related to DFV890 were reported in 7 participants (approximately 10%), of whom 2 participants discontinued the study treatment. These events were of mild and moderate severity, started 5 to 14 days after initiation of DFV890 treatment and resolved within 5 to 16 days after onset.

In summary, there were no unexpected events for this disease indication and patient population. The safety findings are consistent with the early clinical safety profile CCI

Commercially Confidential Information

A Phase 2 study is currently ongoing (CDFV890B12201) in participants with symptomatic knee osteoarthritis

Commercially Confidential Information

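### SAP 7.2 counts each rash in its onset period, so a drug rash on the reported time course falls under follow-up, and no visible rash summary runs from first dose to study completion

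*SAP*

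**What the plan says.** SAP 7.2 (Adverse events) plans a rash table: "The number and percentage of participants with skin rash will be summarized by period". It adds: "Skin rash data will also be listed". The general AE tables are "tabulated by body system and/or preferred term with a breakdown by period", and the drug-related AE tables use the same breakdown. The rule for placing an event is: "An adverse event starting in one period and continuing into the next period is counted only in the onset period".

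SAP 1.4 names the periods: "The study consists of three periods: screening, treatment and follow-up". The protocol summary gives the length of the second: "Treatment period including a second cold challenge (total of 5 days duration". Table 8-1 shows it as Day 1 to Day 5.

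Protocol 1.1.3 and 4.6.3 describe drug-related rash in the completed COVID-19 study. It occurred in 7 participants, about 10%, and "started 5 to 14 days after initiation of DFV890 treatment".

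On the end of collection, protocol 10.1.1 says: "AE monitoring should be continued until the end of the study visit". Table 8-1 allows the Study completion visit from Day 14 to Day 21. Section 9.2 keeps the 30-day safety call in source documents, with serious events reported.

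**The concern.** Safety is a secondary objective. Skin rash is the first drug risk discussed in the protocol (4.6.3), and it has its own unscheduled visit and its own SAP table. A reader who wants to know whether the drug causes rash will look first at the treatment column. If rash follows the timing that the sponsor reports, it starts after that column has closed. With about 6 participants, and at most 10, the placement of one rash changes the message of the table.

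The columns also differ greatly in length. AEs count from informed consent, and screening can last 6 months, or 12 with a historical cold challenge. It includes an untreated challenge in a disease that itself causes rash, and the visible SAP does not limit the rash table to rash unrelated to FCAS. A percentage by period therefore sets a long untreated span beside five days on drug.

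The visible SAP gives neither calendar limits for the AE periods nor a treatment-emergent window. Table 8-1 puts the unscheduled rash visit (105) in the open-label treatment epoch, although protocol section 3 has participants report rash up to the Study completion visit. Two programmers could place the same Day 9 rash in different columns.

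**Working it through.** **Inputs.**
- Treatment period: Day 1 to 5 (protocol summary; Table 8-1).
- Last dose: Day 4 (protocol 6.1.3).
- Rash onset: 5 to 14 days after initiation, 7 participants (protocol 1.1.3).
- Exposed in that study: 70, at 50 mg b.i.d. for 14 days (protocol 1.1.3).
- Study completion visit: Day 14 to 21 (Table 8-1).
- One-day delay option: last dose on Day 5, which moves discharge to about Day 6 (protocol 6.5).

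**Reproducing the plan's figures.** 7/70 = 10.0%, as stated (exact 95% interval 4.1% to 19.5%). The protocol counts k days after Day d as Day d + k: 4 + 10 = 14 for the completion visit and 4 + 30 = 34 for the safety contact. Both match Table 8-1.

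**Onset range in study days.** 1 + 5 = 6 and 1 + 14 = 15, so Day 6 to Day 15, which is ten onset days.

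**Where those ten days fall.**

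| Case | Treatment column | Follow-up column | After the completion visit |
|---|---|---|---|
| Standard, visit on Day 14 | 0 | 9 | 1 (Day 15) |
| Standard, visit on Day 15 to 21 | 0 | 10 | 0 |
| One-day delay, visit 10 days after last dose (Day 15) | 1 (Day 6) | 9 | 0 |
| Range read as study days 5 to 14, standard schedule | 1 (Day 5) | 9 | 0 |

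**With a combined column** (treatment plus follow-up), the standard schedule captures 0 + 9 = 9 of 10 onset days with a Day 14 visit, and 10 of 10 with a visit on Day 15 to 21.

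**Chance that the issue arises.** P(at least one rash) = 1 − (1 − p)^n, with p assumed.
- n = 6: p = 5%, 1 − 0.95^6 = 27%; p = 10%, 1 − 0.90^6 = 47%; p = 15%, 1 − 0.85^6 = 62%.
- n = 10: 40%, 65% and 80%.

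These are illustrative. The 10% comes from another dose, 14 days of dosing and another population.

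**Length of the columns.** Table 8-1 allows the Screening visit from Day −183 to Day −11. Screening therefore lasts 11 to 183 days against 5 days of treatment: 11/5 = 2.2 times to 183/5 = 37 times as long, and more with a historical challenge. The two challenge stays are equal: Day −10 to −8 and Day 3 to 5, three days each.

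**The case against.** The strongest reply is that nothing is hidden. Follow-up is one of the three periods, so a Day 6 to 15 rash has its own column. It would also appear in the rash listing, in the by-participant AE display and, if judged related, in the drug-related table. With 6 to 10 participants a reader can see every case. SAP 7.2 also plans registry tables of treatment-emergent events that are not described as split by period. All of this stands, and it limits the point to presentation. It does not supply a rash summary from first dose to completion, and the visible text gives the registry tables no window. Parts of the SAP are blacked out, so this is a statement about the visible text only.

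A reader might infer that the treatment column cannot show drug rash, or would report 0% whatever the drug does. The documents do not support that. The range comes from 7 participants on another regimen, other rash data are redacted, and protocol 9.1.1 foresees non-FCAS rash during dosing. The one-day delay also puts Day 6 inside treatment.

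A reader might also infer that AE collection misses the rash. At most Day 15 is exposed, only for non-serious events and only if the completion visit falls on Day 14. Serious events run to 30 days after the last dose, and Table 8-1 has an as-required AE entry in its post-treatment part, although the extracted layout does not show which column it covers.

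Finally, a reader might want to say how much busier the screening column will look. The documents give no background AE rate, so only the unequal lengths can be stated. The SAP plans no formal comparison between periods, and it already tabulates AEs related to the cold challenge by period.

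**Conclusion.** The point holds as a reporting weakness that is cheap to remove. On the standard schedule, a rash with the reported onset is counted under follow-up (0 of 10 onset days in the treatment column), and no visible rash summary joins treatment to follow-up. The treatment column could then read as rash-free beside a rash the drug had caused. Percentages by period are not comparable between screening and treatment, because the columns differ in length by about 2 to 37 times, or more with a historical challenge.

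This rests on three assumptions: that AE periods follow the Day 1 to 5 treatment period, that onset follows the earlier study, and that the blacked-out SAP text holds no combined summary. The primary analysis is not affected, and no event is lost from the listings.

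**What to change.** In SAP 7.2:

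1. Add a column from first dose through study completion (treatment plus follow-up) to the skin rash, overall AE and drug-related AE tables. Use the same window to define treatment-emergent in the registry tables.
2. Give the calendar limits of each AE period. State that the onset date sets the period of an AE, including a rash found at unscheduled visit 105.
3. If screening and treatment AEs are compared, show them over matched windows, from challenge admission to discharge in each period.

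In the protocol, reconcile section 10.1.1, section 9.2 and the post-treatment AE entry in Table 8-1 on when collection of non-serious AEs ends.

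Items 1 to 3 cost SAP text and a few extra table columns, with no new data. The reconciliation is a clarification of wording. Recording non-serious AEs in the eCRF at the Day 34 contact is not requested. It would need a protocol amendment (section 14.1) to close a conditional one-day gap.
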